10.9 Liability and Insurance

The Sponsor will take out reasonable third-party liability insurance cover in accordance with all local legal requirements. The civil liability of the Investigator, the persons instructed by the Investigator and the hospital, practice or institute in which they are employed and the liability of the Sponsor with respect to financial loss due to personal injury and other damage that may arise as a result of the carrying out of this study are governed by the applicable law.

The Sponsor will arrange for patients participating in this study to be insured against financial loss due to personal injury caused by the pharmaceutical products being tested or by medical steps taken in the course of the study.

10.10 Publication of Data and Protection of Trade Secrets

Regardless of the outcome of the trial, the Sponsor is dedicated to openly providing information on the trial to healthcare professionals and to the public, at scientific congresses and in peer-reviewed journals. The Sponsor will comply with all requirements for disclosure of study results in appropriate government registries such as ClinicalTrials.gov and EudraCT, as applicable.

The Investigator must agree to submit for review and approval all manuscripts or abstracts/posters to the Sponsor prior to submission for publication or presentation. This allows the Sponsor to protect proprietary information and to provide comments based on information from other studies that may not be available to the Investigator.

Appendix 1 (b) (4)

(b) (4)

(b) (4)

(b) (4)

(b) (4)

AUTHORIZATION: I, the undersigned, declare that I have reviewed the statistical analysis plan along with TLF mock-ups and that to the best of my knowledge the document accurately reflects the protocol objectives.

Authorized by:

(b) (4)

REVISION HISTORY

Version	Date	(b) (4)	Reasons
1.0	APR 20, 2022	(b) (4)	
1. Changes in versions, MedDRA-25.0 and WHODD- WHODRUG B3 SEP2019.2. Anticipated list of TLFs has been updated.3. Added the two new listings for derived endpoint variables (CGM and SMBG).4. Updated the section “Subgroup Analysis (7.1.11.)” due to the addition of one subgroup (Patients ages 2-6 years old) for two endpoints.5. Updated the section “Safety Analysis (7.1.8.)” by adding a table of Vitals Abnormality.6. Updated the section “Analysis Population (6.1)” with the modification of Per Protocol Population definition.7. Updated the section “Efficacy Analysis” with addition of percent change summary and analysis for two efficacy endpoints.

LIST OF ABBREVIATIONS

Abbreviation or special term	Explanation
ADA	Anti-drug antibody
AE	Adverse event
ALT	Alanine aminotransferase
AM	Ante Meridiem
AOC	Area over the curve
AST	Aspartate aminotransferase
AUC	Area under the curve
CGM	Continuous glucose monitoring
CHI	Congenital hyperinsulinism
cm	Centimeters
CS	Clinically significant
CV	Coefficient of variation
DERC	Dose Escalation Review Committee
dL	Deciliter
ECG	Electrocardiogram
eCRF	Case report form
FFA	Free fatty acids
HbA1c	Hemoglobin A1c
Kg	Kilograms

Abbreviation or special term	Explanation
MedDRA	Medical Dictionary for Regulatory Activities
mg	Milligram
mL	Milliliter
msec	Millisecond
NCS	Not clinically significant
PD	Pharmacodynamics
PK	Pharmacokinetics
TLF	Table, Listing and Figure
PM	Post Meridiem
POC	Point of care
RTSM	Randomization and Trail Supply Management
SAE	Serious adverse event
SD	Standard deviation
SE	Standard Error
SoC	Standard of care
SOC	System Organ Class
SMBG	Self-Monitoring of Blood Glucose
TEAE	Treatment emergent adverse event

1. INTRODUCTION

Insulin, secreted by the β cells of the Islets of Langerhans in the pancreas, is the major hormone for lowering blood glucose levels in the fasting and postprandial states. Abnormal elevations in insulin secretion can lead to profound hypoglycemia with cerebral damage and even death. Thus, under normal conditions, the control of insulin secretion is highly regulated to prevent hypoglycemia. Overproduction of insulin results in hyperinsulinemic hypoglycemia, characteristic of diseases such as CHI and post-gastric bypass hypoglycemia (PGBH). Congenital hyperinsulinism (CHI) is the most common cause of recurrent hypoglycemia in neonates and infants.

Diminution of insulin action at target tissues may represent a novel therapeutic approach for the treatment of conditions associated with hyperinsulinism. RZ358, previously referred to as XOMA-358 or XMetD, is a fully human immunoglobulin G, subclass 2 (IgG2) mAb that binds with high potency and selectivity to an allosteric site on the insulin receptor (INSR), acting as a negative modulator of insulin action on target cells by attenuating both the binding of insulin and its downstream signaling.

This statistical analysis plan (SAP) describes the statistical methods and data handling procedures to be followed during the final reporting and analyses of data collected for the study Protocol RZ358-606.

This SAP should be read in conjunction with the study protocol and case report form (CRF). This version of the plan has been developed using the protocol: RZ358-606, version amendment 5.0, dated 17MAR2021 and RZ358-606, version amendment 5.0 US, dated 15MAR2021 and eCRF: version 3.40, dated 04JUN2021.

This study aims to evaluate the safety, tolerability, pharmacokinetics, pharmacodynamics, and glycemic efficacy of multiple ascending doses of RZ358 over 8 weeks in patients with hyperinsulinemic hypoglycemia due to congenital hyperinsulinism (CHI).

2. STUDY DETAILS

2.1. Study Objectives

The objectives of this study are to evaluate the safety, tolerability, PK, PD, and glycemic efficacy of multiple ascending doses of RZ358 over 8 weeks in patients with hyperinsulinemic hypoglycemia due to CHI.

2.2. Study Design

This is a Phase 2, multi-center, open-label, multiple ascending dose study to evaluate the safety, tolerability, PK, PD, and glycemic efficacy of RZ358 in patients with hypoglycemia due to CHI. The

study will consist of up to 4 dose cohorts, which are to be enrolled independently and conducted sequentially, comprised of up to 6-8 patients per cohort to ensure each cohort includes at least 3 patients aged \leq 10 years. Eligible patients will be successively enrolled into the cohort that is open for enrollment at that time, at the lowest dosing cohort that is yet to be filled.

In Cohorts 1, 2, and 3 the dose amount will be fixed during the entire 8-week Treatment Period, while in Cohort 4 there will be a scheduled bi-weekly dose-titration for the first 4 weeks, followed by a fixed dose amount thereafter for the remaining 4 weeks. The Sponsor may decide to add a cohort to repeat a dose level or to study an additional dose level, but the dose level for any cohort will not exceed the planned dose level for that cohort, as specified in this protocol.

Advancement to subsequent cohorts will not occur until at least 4 patients from the prior cohort have each received at least 4 weeks of study drug (2 bi-weekly doses), without safety concerns. A Dose Escalation Review Committee will assess all available and relevant interim data from each cohort to determine the appropriateness of dose escalation to a new cohort.

Table 1: Study Design/Cohort Dosing Regimens

Cohort	Dosing (mg/kg)			
	Wk 1	Wk 3	Wk 5	Wk 7
1	3	3	3	3
2	6	6	6	6
3	9	9	9	9
4	3	6	9	9

Following informed consent, patients will complete a Screening Period to determine eligibility. After the preliminary screening assessment, patients who are otherwise eligible will undergo scheduled self-monitoring of blood glucose (SMBG) by point of care (POC) glucometer as well as have a CGM sensor placed according to the instruction manual, for completion of a minimum 10-day outpatient CGM evaluation to assess glycemic eligibility and establish a baseline. (b) (4)

patients will use an SMBG for their POC throughout the trial. Patients taking existing and stable doses of standard of care (SoC) medications or nutritional supplementation for CHI at the time of screening should continue the same regimen and doses throughout this period.

(b) (4)

(b) (4)

To meet glycemic qualification criteria, patients must have glucose values <70 mg/dL (3.9 mmol/L) for $\geq 4\%$ of the overall monitored CGM time with at least 3 severe hypoglycemia events by CGM threshold of <50 mg/dL (2.78 mmol/L) during the last 7 days of a 10-day CGM evaluation period AND be experiencing ≥ 3 hypoglycemia events (<70 mg/dL) per week by SMBG and/or according to the Investigator's evaluation (b) (4)

During the Screening Period and throughout the study, patients will be requested to follow their usual diet (including enteral feeding, as applicable) and activity level, as evaluated and instructed by qualified study personnel.

At the conclusion of the CGM and glycemic eligibility evaluation, final eligibility will be determined, and fully eligible patients will check in to the inpatient facility on Day -1, to begin the Treatment Period. On Day -1, patients will begin a 12h baseline fasting challenge evaluation, which will conclude prior to Day 1 dosing. Re-screening may be permitted under certain extenuating circumstances (e.g. laboratory outlier suggesting result artifact, insufficient duration of CGM collection), only with pre-approval by the Sponsor.

Beginning at Day 1 of the Treatment Period, patients will receive study drug via IV infusion every 2 weeks over an 8 week total Treatment Period. Thus, patients who complete the entire Treatment Period will receive 4 doses of study drug over a total of 8 weeks. Patients will remain under inpatient observation for at least 48h following dosing on Week 1, and for at least 24h following dosing on Weeks 3, 5, and 7, for completion of PK blood sampling and safety assessments. Throughout the Treatment Period and through post-treatment follow-up Day 42 after the patient's final dose in the study (cumulative study Day 85), glucose levels will be assessed and recorded by CGM. (b) (4)

All patients will continue to use an SMBG as their POC throughout the trial.

Throughout the Treatment period and through the End of Treatment (EOT) visit on post-treatment follow-up Day 14 (cumulative study Day 57), SMBG by POC glucometer must be performed (b) (4)

In addition, SMBG by POC glucometer should be performed to confirm suspected hypoglycemia (by

CGM or symptoms) prior to implementing rescue measures. (b) (4)

Thereafter, during the remainder of the Follow-up period, CGM and scheduled SMBG by POC glucometer will be stopped, but the latter may continue to be performed and recorded in the diary at the discretion of the patient and/or Investigator.

(b) (4)
(b) (4)

[figure not shown]
Otherwise, changes in the dose or regimen of background SoC therapies should not occur, except in the event that hypo- or hyperglycemic rescue criteria are met, or changes are deemed medically necessary by the Investigator. (b) (4)

At the conclusion of Week 7 dosing and discharge from the clinic, each patient will complete outpatient post-treatment follow-up visits at Days 14 (EOT), 28, and 42 (each ± 3 days), and a final End of Study (EOS) follow-up visit on Day 105 (+3 days) for purposes of evaluating extended PK and safety over a period of 5 half-lives of the study drug.

Protocol versions 1.0, 2.0, and 3.0 were never implemented. Prior to implementing protocol version amendment 5.0, three patients in Cohort 1 were enrolled and treated under protocol version amendment 4.0, which differed from version 5.0 in dosing regimen (frequency) and the glucose entry criterion by CGM, as noted below:

1. To meet glycemic qualification criteria, patients must have glucose values <70 mg/dL (3.9 mmol/L) for $\ge 8\%$ of the overall monitored time and for ≥ 60 min per day on at least 5 of the 10 CGM evaluation days AND be experiencing ≥ 3 hypoglycemia events (<70 mg/dL) per week by SMBG and/or according to the Investigator's evaluation.
2. Beginning at Day 1 of the Treatment Period, patients will receive study drug via IV infusion weekly for the first 4 weeks (induction dosing), followed by subsequent infusions every 2 weeks for an additional 4 weeks (maintenance dosing). Thus, patients who complete the entire Treatment Period will receive 6 doses of study drug over a total of 8 weeks.

Figure 1: Study Design

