The number and percentage of patients with missing values for a variable/category/event will also be presented for the resulting visits/time points under the “Missing” category. Percentage will be obtained by: % = $(n/N) * 100$. Unless otherwise stated, all percentages will be expressed to one decimal place. P-value will be presented three decimal places or P-value closer to zero will be presented as <0.001 and p-value closer to one will be presented as >0.999.

The following conventions will be applied to analyses/data presentation:

All dates will be displayed in DDMMYY format.

Unscheduled data for assessments that are specific to a discrete visit (rather than continuously measured e.g., SMBG or CGM) will be presented in Listings but not in Tables and Figures, unless missing data imputation rules (windows) are met, as described below.

Prior to implementing protocol version amendment 5.0, three patients in Cohort 1 were enrolled and treated under protocol version amendment 4.0, which differed from version 5.0 in dosing regimen (frequency) so, the following visit mapping will be followed for efficacy analysis, considering the dosing period:

“Subjects who were enrolled in Cohort 1 under protocol version amendment 4.0, their Week 1 and Week 2 data are aggregated and reported under '2 Weeks' timepoint. Similarly, Week 3, Week 4 and Week 5 data are aggregated and reported under '4 Weeks', their Week 6 and Week 7 are aggregated and reported under '6 Weeks', their Week 8 and Week 9 data are aggregated and reported under '8 Weeks/EOT' timepoint.”

Handling of Missing Data

If the Adverse Event Relationship flag is missing, the relationship for adverse event will be imputed and will be considered as “Related”. If the Adverse Event Severity grade is missing, the severity will be imputed and will be considered as “Severe”. To handle missing or partial AEs and concomitant medication dates, the following rules will be applied.

For partial AE/CM Onset/Start Date:

1. If the year is unknown, then do not impute the date but assign a missing value.

Missing day and month

If the year is same as the year of first day on study medication, then the day and month of the start date of study medication will be assigned to the missing fields.

If the year is prior to the year of first day on study medication, then December 31 will be assigned to the missing fields.

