6.2. Treatment Groups

The study will consist of up to 4 dose cohorts, which are to be enrolled independently and conducted sequentially, comprised of up to 6-8 patients per cohort to ensure each cohort includes at least 3 patients aged ≤ 10 years with hypoglycemia due to CHI.

In Cohorts 1, 2, and 3 the dose amount will be fixed during the entire 8-week Treatment Period, while in Cohort 4 there will be a scheduled bi-weekly dose-titration for the first 4 weeks, followed by a fixed dose amount thereafter for the remaining 4 weeks. (Refer [section 2.2](#), Table 1: Study Design/Cohort Dosing Regimens).

The cohorts will be labelled in the TLFs as Cohort 1 (3 mg/kg), Cohort 2 (6 mg/kg), Cohort 3 (9 mg/kg), Cohort 4 (Dose Escalation mg/kg), and RZ358 Total.

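### Cohort 1 estimates mix three Amendment 4.0 patients (6 planned infusions, a different CGM entry rule) with Amendment 5.0 patients (4 infusions), and no readable part of the SAP gives Cohort 1 without them

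*SAP*

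**What the plan says.** SAP 2.2 states that "three patients in Cohort 1 were enrolled and treated under protocol version amendment 4.0, which differed from version 5.0 in dosing regimen (frequency") and in the CGM entry criterion.

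- **Dosing.** Amendment 4.0 gave weekly infusions for four weeks, then one every two weeks for four weeks: "Thus, patients who complete the entire Treatment Period will receive 6 doses of study drug over a total of 8 weeks". SAP Table 1 defines Cohort 1 as four infusions, in Weeks 1, 3, 5 and 7.
- **Entry rule.** Amendment 4.0 required glucose below 70 mg/dL for at least 8% of monitored time, and for at least 60 "min per day on at least 5 of the 10 CGM evaluation days". The current rule requires at least 4% of time below 70 mg/dL, with "at least 3 severe hypoglycemia events by CGM threshold of <50 mg/dL (2.78 mmol/L) during the last 7 days" of the screening period.
- **Handling.** SAP 3 says that "the following visit mapping will be followed for efficacy analysis, considering the dosing period". Weeks 1-2 become the 2-week point. For the 4-week point, "Week 3, Week 4 and Week 5 data are aggregated and reported under" that label. Weeks 6-7 become the 6-week point. For 8 Weeks/EOT, "their Week 8 and Week 9 data are aggregated and reported under" that label. The mapping stands in quotation marks in the SAP, so it may be meant as a table note, but the SAP does not call it one. It gives neither the infusion count nor the entry rule.
- **Display.** SAP 6.2: "The cohorts will be labelled in the TLFs as Cohort 1 (3 mg/kg), Cohort 2 (6 mg/kg), Cohort 3 (9 mg/kg"), with further columns for Cohort 4 and the RZ358 total.

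SAP 6.1 (populations), 7.1.7 (efficacy) and 7.1.13 (changes from the protocol) contain no separate row, exclusion or supportive estimate by protocol version.

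**The concern.** The trial studies ascending doses, and a reader will take the Cohort 1 row as the result for the lowest fixed regimen in Table 1. SAP 7.1.7.1 attaches a 95% CI and a paired-test p-value to that row. If up to half of the patients behind it were planned to receive a more frequent schedule, the row describes a mixture that the column heading does not show.

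The entry rules add a second layer. Neither implies the other: one asks for more time below 70 mg/dL, the other for events below 50 mg/dL. SAP 2.2 uses the screening CGM both for eligibility and to establish the baseline. The two groups were therefore selected differently on the quantity from which change is measured, and may differ in regression to the mean whatever the drug does. The week mapping deals with the timing of visits only.

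**Working it through.** **1. Infusion counts (SAP 2.2).** Amendment 4.0: 4 weeks / 1 + 4 weeks / 2 = 6. Amendment 5.0: 8 weeks / 2 = 4. Both stated figures reproduce.

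**2. Weight of the three patients.** Cohorts have 6-8 patients. 3/8 = 0.375 and 3/6 = 0.50. If their mean change differs from that of the other Cohort 1 patients by D, the Cohort 1 mean moves by 0.375D to 0.50D. For an assumed D of 10 points of time in range, that is 3.75-5.0 points. In the RZ358 total (24-32 patients) the weight is 3/32 to 3/24, or 9.4-12.5%.

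**3. Entry floors for time below 70 mg/dL.** 0.08 × 1440 = 115 min/day; 0.04 × 1440 = 58 min/day. These are floors of two different rules, not measured severity.

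**4. Exposure illustration.** Assumptions: 3 mg/kg at every infusion, one compartment, each dose treated as a bolus. Half-life 105 / 5 = 21 days, because SAP 2.2 describes the Day 105 visit as covering five half-lives. A dose of age s days contributes 2^(−s/21).

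Reference infusions fall on days 1, 15, 29 and 43, with windows 1-15, 15-29, 29-43 and 43-57. On the SAP 3 mapping the Amendment 4.0 windows are 1-15, 15-36, 36-50 and 50-64. The readable text does not give the weeks of the last two Amendment 4.0 infusions, so two schedules are tried:

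- Weeks 6 and 8 (days 1, 8, 15, 22, 36, 50): the EOT window starts at the last dose.
- Weeks 5 and 7 (days 1, 8, 15, 22, 29, 43): the EOT window starts 7 days after the last dose.

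No infusion falls inside an EOT window after its start, and the EOT windows are equally long, so the EOT ratio is the ratio of levels at the start:

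- Reference, day 43: 1 + 0.630 + 0.397 + 0.250 = 2.277.
- Weeks 6 and 8, day 50: 1 + 0.630 + 0.397 + 0.315 + 0.250 + 0.198 = 2.790; ratio 1.23.
- Weeks 5 and 7, day 50: 0.794 + 0.500 + 0.397 + 0.315 + 0.250 + 0.198 = 2.454; ratio 1.08.

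Averaging the summed curves over each window gives:

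| Last two infusions | 2 wk | 4 wk | 6 wk | 8 Weeks/EOT |
|---|---|---|---|---|
| Weeks 6 and 8 | 1.56 | 1.75 | 1.40 | 1.23 |
| Weeks 5 and 7 | 1.56 | 1.98 | 1.58 | 1.08 |

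The EOT ratios (Weeks 6 and 8; Weeks 5 and 7) are 1.14 and 0.91 for a 14-day half-life, and 1.28 and 1.17 for 28 days.

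**5. Precision without the three.** The half-width of the 95% CI for a mean change, in SD units, is t(0.975, n−1)/√n.

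| n | half-width |
|---|---|
| 3 | 4.303/√3 = 2.48 |
| 5 | 2.776/√5 = 1.24 |
| 6 | 2.571/√6 = 1.05 |
| 8 | 2.365/√8 = 0.84 |

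For the three against the other m patients it is t(0.975, m+1) × √(1/3 + 1/m): 2.27 SD for m = 3 and 1.79 SD for m = 5.

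**The case against.** **The mixture is disclosed.** SAP 2.2 sets out both differences and SAP 3 has a dedicated rule. SAP 3 also plans by-patient listings, and the revision history adds listings of derived CGM and SMBG variables. A reader could rebuild the split. This stands: what is missing is a display beside the estimate, not the information itself.

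**A footnote may exist.** The quoted mapping in SAP 3 may be table-note text, and it already writes out the weeks behind each time point. SAP 3 refers to mock tables that were not supplied, and parts of SAP 7.1.11 and 9.1.2 are redacted. A reader might infer that the plan has no footnote and no with/without estimate at all. The documents support only that none is readable.

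**The label may be right.** A reader might infer that 3 mg/kg misstates what these patients received. SAP 2.2 names frequency and entry criterion as the differences, so nothing contradicts 3 mg/kg per infusion. No cohort label gives an infusion count.

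**The consequence is limited where it counts.** SAP 7.1.7.4 sets 8 Weeks/EOT as the time point for the primary endpoint, where the illustrative ratio is modest and could be 1. The larger ratios belong to an intermediate visit. This stands.

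**The remedy is imprecise.** That also stands, and it limits the display to description. It does not justify leaving a known mixture of this weight out of the results tables.

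**Conclusion.** A minor point, upheld in a limited form. Followed as written, the Cohort 1 mean, CI and paired test describe a blend of two planned regimens and two entry rules, with 38-50% of patients from Amendment 4.0 if the cohort reaches 6-8. They do not estimate the four-infusion regimen of Table 1.

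The size of the resulting shift in time in range cannot be derived from the documents. The exposure ratios rest on the assumed model, half-life and infusion weeks. Two further inferences are not supported. The first is that the three patients had materially higher exposure at the primary time point: the 0.91-1.28 range includes no difference. The second is that they were more severely affected: the 8% and 4% floors belong to different rules, and the 4% rule also requires events below 50 mg/dL.

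Protocol 7.1 describes an unpowered proof of concept with p-values for hypothesis generation. This is therefore a matter of reporting and interpretation, not of error control. The facts about the three patients are firm; the absence of a with/without estimate is established only for the readable text.

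**What to change.** 1. In SAP 7.1.7, add a supportive descriptive display of the Cohort 1 primary and key secondary estimates, with 95% CIs, with and without the three Amendment 4.0 patients, in ITT and PP. Omit this if a redacted part of the SAP or the mock tables already contain it.
2. Extend the SAP 3 mapping note, and print it under the Cohort 1 results, to give n = 3, the 6 planned infusions with their scheduled weeks, and the Amendment 4.0 CGM entry rule.

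The cost is one longer note and one extra set of rows on data already collected. The downside is low precision: with 3-5 patients left, the rows can show how far the Cohort 1 result depends on the three but cannot test the difference. They should be labelled descriptive.
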